## 7. TRIAL MONITORING

Representatives of Hologic (or designee) will verify patient data and ensure compliance with clinical protocol and other trial requirements, according to the guidelines set forth in the applicable monitoring Standard Operating Procedures (SOP) and ISO 14155 guidelines to be utilized for the trial.

# 7.1 Monitor Training

Hologic and/or designated monitors will be trained appropriately to monitor trial progress as defined in the Hologic Monitoring Plan.

# 7.2 Site/Investigator Training

Hologic and/or designee will be responsible for providing training to the Investigator and appropriate clinical site personnel.

## 7.3 Site Monitoring

Hologic and/or designee may conduct periodic compliance assessments at the trial site(s). Hologic and/or designee may request access to all trial records including source documentation for inspection during a compliance assessment. The Investigator and research coordinator must be available to respond to reasonable requests and queries made during the compliance assessment process.

# 7.4 Regulatory Agency Inspection

In the event that an investigator is contacted by a regulatory agency regarding this trial, the Investigator will notify Hologic or its designee immediately. The Investigator and research coordinator must be available to respond to reasonable requests and queries made during the inspection process. The investigator must provide Hologic or designee with copies of all correspondence that may affect review of the current trial (e.g., Form FDA 483, Inspectional Observations and Warning Letters). Hologic may provide needed assistance in responding to regulatory audits.

## 8. STATISTICAL CONSIDERATIONS

7 clinical trial sites each with 3 radiologists performing 20 biopsies (10 with local standard-of-care, and 10 with the Brevera Breast Biopsy System, as per randomization procedure) results in a total of 420 subjects enrolled in phase 2. This sample size achieves approximately 80% power to detect a difference in mean procedure time of 3 minutes between the Brevera and standard of care biopsy systems assuming a standard deviation of 12 minutes in procedure time and an intraclass correlation of 0.150 at a standard significance level of alpha=0.05. Mixed effects regression will be utilized to assess the impact of the biopsy device (e.g., Brevera or local standard-of-care) on total procedure time, post-biopsy complication rates and differences in discordant biopsies. For these analyses, biopsy device type, subject physical habitus and lesion location (i.e., "near the chest wall or axilla?" yes/no) will be considered fixed effects, and site and radiologist will be considered random effects. Total tissue acquisition by number of cores, total acquired sample mass, and total tissue utilized by pathology for diagnosis will be compared between the Brevera system and local standard-of-care using Analysis of Variance (ANOVA) testing. Lastly, sub-analyses will be performed to look at specific comparisons between the Brevera system and other biopsy systems if multiple sites utilize the same biopsy system as their standard-of-care device.

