#### 5.4.1 Phase 1 (Run-in Phase)

After obtaining subject informed consent, each radiologist participating in the study will initially use the Brevera Breast Biopsy system for enrollment of his or her first five (5) cases. The run-phase will allow

each participating radiologists to become familiar with the use of a new device. The five (5) cases per radiologist completed will be compared to the Brevera cases completed in Phase 2 for the same outcomes listed in sections 5.2 and 5.3 above so as to provide informational data related to the training and adoption of the Brevera Breast Biopsy System.

Once a clinician has completed his or her initial five (5) run-in cases, they may begin phase 2 of the study. Note that each individual radiologist participating in the study must complete their initial five (5) cases prior to beginning Phase 2; however, each individual participant may complete the initial five (5) cases at different times. Example: it may be expected that the first participating radiologist at a given site may begin in phase 2 while the second and/or third participating radiologist at the same site in the study are still completing their five run-in cases.

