# 5.4.2 Phase 2 (Block Stratification Phase) -

Each individual radiologist will enroll a maximum of twenty (20) subjects, and a maximum of three (3) radiologists may participate in this study from each representative study site. After a radiologist completes his or her five (5) cases with Brevera in Phase (1), each site will begin to sequentially enroll subjects based on a block-stratified randomization. Subjects will either be enrolled to have their biopsy procedure performed using current standard-of-care breast biopsy procedures at the site or Brevera Breast Biopsy procedures based on the block diagram given in Figure.

Randomization of enrollment will be determined prior to study start-up and provided to each site. Each radiologist will enroll 20 total subjects as part of the block stratification phase as defined in Figure 2.

[figure not shown]

Figure 2: Study Design Outline

Case Report Forms related to procedural data and surveys have been created in order to obtain information related to feedback from the clinician(s), patient, and technologist(s). The surveys include questions that relate to the overall feel and aesthetic of the product as well at the overall performance of the breast biopsy system. The questionnaires will be given to the clinician(s), patient, and the technologist(s) at the conclusion of the procedure and will be focused for each target group. Once a patient has completed the breast biopsy procedure, her direct participation in the trial is concluded. There are no follow-up visits required for participation in this trial..

Surveys will be collected via paper forms to capture the questionnaire data, and subsequently abstracted into an Electronic Data Capture (EDC) system. The results of the survey questions and images obtained will be compiled and used to support marketing claims and publications, as applicable.

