#### 6. TRIAL PROCEDURES

The trial will collect de-identified case report form data and patient images from biopsy procedures. This will include collection of images from the prior exam leading up to the breast biopsy procedure. The biopsy procedures will be done consistent with current clinician direction/standard-of-care.

Prior to use of the new Brevera Breast Biopsy System, normal applications training will take place in order to train the users on new features and quality control testing.

Patients will be enrolled using a block randomization. Each clinician will complete ten (10) patients in block 1 and ten (10) patients in block 2. (Blocks will be defined as either the Standard-of-care biopsy system or the Brevera Biopsy system). A clinician must complete block 1 before moving on to block 2.

[figure not shown]
Clinical data will be collected on the procedure within each block by patient procedure. The procedures will collect data related to time of procedure, number of cores collected, post biopsy results and survey data on the system.

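### The section 8 procedure-time model omits block position, so if the two block orders are uneven across radiologists, a time shift common to both devices enters the device effect

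*Combined protocol and SAP*

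**What the plan says.** Section 6 (Trial Procedures) sets the layout within a radiologist: "Each clinician will complete ten (10) patients in block 1 and ten (10) patients in block 2". Each block is a single device: "Blocks will be defined as either the Standard-of-care biopsy system or the Brevera Biopsy system". The sequence is strict: "A clinician must complete block 1 before moving on to block 2".

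Section 5.4.2 (Phase 2) says of the allocation: "Randomization of enrollment will be determined prior to study start-up and provided to each site". It refers to a diagram for the layout, with subjects assigned to standard of care or to "Brevera Breast Biopsy procedures based on the block diagram given in Figure". That figure, and another that follows the block rule in section 6, are not shown in the text reviewed. The readable text does not say whether order is randomised by radiologist or by site, or whether the two orders are to be balanced.

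Section 8 plans for "7 clinical trial sites each with 3 radiologists performing 20 biopsies (10 with local standard-of-care, and 10 with the Brevera Breast Biopsy System") and specifies mixed effects regression for procedure time. Its sentence on model terms begins "For these analyses, biopsy device type, subject physical habitus and lesion location"; these three are the fixed effects, and site and radiologist are random. No term for block position, sequence or calendar time is listed.

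Before Phase 2 there is a run-in (section 5.4.1): "each radiologist participating in the study will initially use the Brevera Breast Biopsy system for enrollment of his or her first five (5) cases".

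**The concern.** At radiologist level this is a two-period crossover with ten cases per period. A radiologist's device difference is also that radiologist's difference between later and earlier cases. Only the mix of orders across radiologists separates device from time.

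The random radiologist effect does not help, because it is the same in both blocks and cannot absorb a change between them. If procedures become generally faster or slower from block 1 to block 2, for instance as staff get used to trial timing and forms, and more radiologists have one order than the other, part of that change is credited to the device. The comparison at stake is the primary endpoint.

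**Working it through.** **Inputs.** From section 8: 7 sites × 3 radiologists = 21 radiologists; 10 + 10 cases each, so 210 per device and 420 in all; SD 12 min; intraclass correlation 0.150; alpha 0.05 (two-sided assumed, as sidedness is not stated); target difference 3 min; power about 80%. Assumed, because the documents give no figure: a shift t from block 1 to block 2 of 1, 2 or 3 min, common to both devices and all radiologists.

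**Step 1: reproduce the stated power.** The device comparison is within radiologist, so the between-radiologist share of variance drops out:

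SE = 12 × √(1 − 0.15) × √(2/210) = 1.080 min

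Power = Φ(3/1.080 − 1.96) = 79.35%, which agrees with the stated figure of about 80%.

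**Step 2: bias without a block term.** A radiologist who uses Brevera second contributes (device effect + t); one who uses Brevera first contributes (device effect − t). With k of 21 using Brevera second, the average is the device effect plus

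bias = t × (2k − 21)/21.

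Type I error for a given split = 1 − Φ(1.96 − bias/SE) + Φ(−1.96 − bias/SE), with SE held at 1.080.

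**Step 3: cost of adding the term.** The variance of the device effect is multiplied by 1/(1 − imbalance²), and power is recomputed with the larger SE.

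| Order split | Imbalance | Bias, t = 1 / 2 / 3 min | Type I error, no block term | Variance factor with term | Power with term |
|---|---|---|---|---|---|
| 11:10 | 1/21 = 0.048 | 0.05 / 0.10 / 0.14 min | 5.0 / 5.1 / 5.2% | 1.002 | 79.3% |
| 12:9 | 3/21 = 0.143 | 0.14 / 0.29 / 0.43 min | 5.2 / 5.8 / 6.8% | 1.021 | 78.5% |
| 14:7 | 7/21 = 0.333 | 0.33 / 0.67 / 1.00 min | 6.1 / 9.5 / 15.3% | 1.125 | 74.5% |
| 21:0 | 1 | 1 / 2 / 3 min | 15.3 / 45.7 / 79.4% | not separable | none |

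**Step 4: average over simple randomisation by radiologist.** With k binomial(21, ½), the mean bias is 0 and its SD is t/√21 = 0.22 / 0.44 / 0.65 min. Averaging the type I error over k gives 5.5% / 6.9% / 9.4%. The chance of a split of 14:7 or worse is 18.9%.

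**The case against.** **Balance may already be in the plan.** A reader might infer that the plan leaves block order unbalanced. The documents do not support that: section 5.4.2 refers to a diagram that was not available, and it could show balanced orders. Nor does any readable text say that all radiologists share one order, so the 21:0 row is a limit, not a finding. The missing model term does not depend on the figure.

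**The order is described as randomised.** A reader might also infer a systematic bias for or against Brevera. If order is randomised at equal odds, the expected bias is zero. What remains is an error conditional on the realised split. Once the list is drawn, that error is fixed for this trial and its confidence interval does not allow for it. But its direction is not predetermined, and at 11:10 it is negligible.

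**The sizes are assumed.** This stands. The shifts of 1 to 3 minutes have no source in the documents, and the largest equals the whole target difference. Unconstrained randomisation is assumed too. Setting order by site (7 units) would raise the average type I error to 6.4% / 10.9% / 17.8%. Section 5.4.2 does send the list to sites, but section 6 defines blocks by clinician and the unit is not stated, so those figures are only a possibility.

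**Learning is partly dealt with.** Five Brevera run-in cases per radiologist, training, and investigators already experienced in core biopsy all reduce early learning. Any remaining Brevera-specific learning is not a shift common to both devices, and a block-position main effect would not remove it. Staggered starts also mean that a one-off calendar change would not fall uniformly between block 1 and block 2.

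**Conclusion.** The point holds conditionally. Sequential single-device blocks and a model without block position mean that order imbalance passes a common time shift into the primary device estimate in proportion to the imbalance. For the assumed shifts, the effect is trivial at 11:10. At 14:7 it reaches up to a third of the 3-minute target. Under simple randomisation by radiologist, average type I error is moderately above 5%. Neither an unbalanced order nor an actual bias is shown by the documents.

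The figures rest on all 21 radiologists completing both blocks, a shift common to all of them, no radiologist-specific drift, no variation in the device effect between radiologists, and a two-sided normal test. The point is worth acting on because it concerns the primary endpoint and the remedy costs little when orders are near balance.

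**What to change.** 1. In section 8, add block position (first or second) as a fixed effect in the procedure-time model.
2. In section 5.4.2, state the unit of the block-order randomisation, and confirm or constrain the list prepared before start-up so that the two orders are as equal as possible across participating radiologists. That is 11:10 if there are 21. Word it for whatever number takes part, since three radiologists per site is a maximum and the synopsis allows up to ten sites. If the block diagram already does this, one sentence saying so is enough.

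The two changes belong together. At 11:10 the term uses one degree of freedom and adds about 0.2% to the variance (power 79.35% to 79.3%). At 14:7 it adds 12.5% (power 74.5%). If every radiologist had the same order, the term could not be separated from device at all. It removes a common shift only, and leaves Brevera-specific learning and radiologist-specific drift where they are.

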The Brevera breast biopsy system with CorLumina imaging technology also has the capability to display images as well as to transfer these images to external devices. The images acquired with this system are intended to confirm removal of tissue from a suspected lesion or pathology. The system is not intended for diagnostic purposes.

Radiology technologists, surgical personnel, surgeons, radiologists, and pathologists can use the specimen radiography equipment in the Brevera breast biopsy system with CorLumina imaging technology.

[figure not shown]

Figure 1: Brevera Breast Biopsy System with CorLumina Imaging Technology System

Overview

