## 5.4 Trial Design

Prospective, multi-center, block stratified controlled clinical trial. This trial will include collection of the breast imaging exams (both screening and diagnostic work up) leading up to the breast biopsy procedure, which may include mammograms, ultrasound or MRI images as applicable.

The trial procedure will roll out in two phases: 1) a run-in phase consisting of five (5) procedures aimed at familiarizing participating radiologists with the Brevera Breast Biopsy System; and 2) an analysis phase consisting of a block-randomized acquisition of twenty (20) sequential acquisitions utilizing both standard-of-care biopsy system at each site and the Brevera Breast Biopsy System.

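### The procedure-time model could cheaply gain precision and some case-mix control by adding type and size of the finding, read from images that already exist; the stated power stands without them.

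*Combined protocol and SAP*

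**What the plan says.** - **Model.** Section 8 plans a mixed effects regression for procedure time, complication rates and discordant biopsies. The fixed effects are "biopsy device type, subject physical habitus and lesion location". Location is a single yes/no item on closeness to the chest wall or axilla. Site and radiologist are random effects.
- **Sample size.** Seven sites with three radiologists doing 20 biopsies each "results in a total of 420 subjects enrolled in phase 2", split within radiologist as "10 with local standard-of-care, and 10 with the Brevera Breast Biopsy System". Section 8 continues: "This sample size achieves approximately 80% power" to "detect a difference in mean procedure time of 3 minutes", "assuming a standard deviation of 12 minutes in procedure time" and an intraclass correlation of 0.150, at alpha 0.05.
- **Images.** Section 5.4 states: "This trial will include collection of the breast imaging exams (both screening and diagnostic work up) leading up to the breast biopsy procedure". Section 6 repeats this, and inclusion criterion 2 (Section 5.7.1) requires a finding for which images are available.
- **Feature under test.** The primary endpoint (Section 5.2) compares procedure time with and without the system's real-time imaging. Section 2.2 says of that imaging: "The images acquired with this system are intended to confirm removal of tissue from a suspected lesion or pathology".
- **Allocation.** Under Section 6 each clinician finishes ten patients on one device before starting ten on the other. Under Section 5.4.2 the allocation is fixed before start-up and given to each site.

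No section puts type or size of finding into the model, stratifies on either, or plans a sensitivity analysis with them.

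**The concern.** The plan already accepts that patient and lesion difficulty should be adjusted for, but it describes the lesion only by whether it lies in an awkward place. Sampling time, and the time needed to confirm that the target was removed, plausibly also depend on what the target is and how large it is. Both could be known before the procedure.

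Two things are at stake. The first is precision: variance that these terms explain would leave the residual, and the design has little to spare at 80% power. The second is case mix. Patients are not allocated one at a time within a radiologist, and the site knows which device comes next. If the kind of finding enrolled differs between a radiologist's two runs, the difference falls on the device comparison. The radiologist random effect removes differences between operators, not a shift between one operator's runs.

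**Working it through.** **Inputs from Section 8.** 210 biopsies per device (7 × 3 × 10), difference 3 minutes, SD 12 minutes, intraclass correlation 0.150, alpha 0.05. Sidedness is not stated, so two-sided is assumed. The correlation is read as the between-radiologist share of variance. It drops out of the comparison because each radiologist uses both devices.

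**Step 1: reproduce the stated power.**
- Residual SD = 12 × √(1 − 0.15) = 11.06 minutes; residual variance = 144 × 0.85 = 122.4.
- SE of the device difference = 11.06 × √(2/210) = 1.08 minutes.
- Power = Φ(3/1.08 − 1.96) = 79.4%, or 79.2% with a t distribution on 398 degrees of freedom.

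This agrees with the stated figure of about 80%. All residual variance is counted, including whatever is due to type and size of finding, and no credit is taken for habitus or location.

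**Step 2: add type and size.** Let R² be the share of within-radiologist variance they explain beyond the covariates already planned. The documents give no value, so a range is assumed. SE = 12 × √(0.85 × (1 − R²)) × √(2/210), and the sample size without the covariates that gives the same precision is 420/(1 − R²).

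| R² (assumed) | SE (min) | Power at 3 min | Equivalent Phase 2 size |
|---|---|---|---|
| 0% | 1.08 | 79.4% | 420 |
| 2% | 1.07 | 80.2% | 429 |
| 5% | 1.05 | 81.4% | 442 |
| 10% | 1.02 | 83.4% | 467 |
| 20% | 0.97 | 87.4% | 525 |

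For scale, suppose a finding type is present in 40% of cases (assumed). A 5-minute effect on time has variance 25 × 0.4 × 0.6 = 6, and 6/122.4 = 5%. A 10-minute effect has variance 24, and 24/122.4 = 20%.

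**Step 3: chance imbalance is already counted.** For that 40% type, the SD of the difference in its proportion between devices is √(2 × 0.4 × 0.6/210) = 0.048. A 10-minute effect turns this into 0.48 minutes. But 1.08 × √0.196 is also 0.48, where 0.196 = 24/122.4. So this is the 20% row seen another way and lies inside the 1.08-minute SE.

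**Step 4: systematic shift between runs.** If the mix differs on average between the two devices' runs, bias = time difference between types × difference in proportion. All values here are assumed, and the error rates use the 1.08-minute SE.

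| Time difference | Shift in proportion | Bias | Two-sided type I error |
|---|---|---|---|
| 5 min | 10 points | 0.5 min | 7.5% |
| 5 min | 20 points | 1.0 min | 15% |
| 10 min | 20 points | 2.0 min | 46% |

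For a type at 50% prevalence the chance SD is √(0.5/210) = 4.9 points. A 20-point shift is therefore about 4.1 SDs and would need selective enrolment, not chance. Nothing in the documents shows that such a shift occurs.

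**The case against.** The strongest reply is that this is a preference. The plan pre-specifies two patient-level covariates and two random effects, and a randomised comparison need not adjust for every plausible predictor. No document shows that type or size predicts procedure time, and at an R² of 2% the gain is under one point. This stands, and it is why the point is a suggested improvement.

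A reader might infer that leaving the terms out pushes power below its target. It does not. The 79.4% already carries that variance, so the omission only forgoes a gain. The 79.4% is also conservative: if habitus and location alone explained 1.7% of within-radiologist variance, power would be 80.0%. A reader might also add the 0.48 minutes of chance imbalance to the SE; Step 3 shows that this counts it twice.

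Two further objections are partly right. Section 2.2 ties the study device to stereotactic or tomosynthesis guidance, and Section 5.7 speaks of mammographic findings, so the mix may be narrower than the synopsis and Section 5.7.1 suggest. Even so, none of these sections limits type or size. Next, images are collected as applicable across modalities and no section plans a reading of them, so the fix needs a recording rule. The case report forms are not in the documents, and the fields may already exist. They would still be absent from the model.

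Finally, if the imaging helps more for some targets than others, that is an interaction between device and finding type. Main effects do not test it, and this point does not claim that they would.

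**Conclusion.** The omission is real and inexpensive to mend, but it is not an error and the power statement stands. The likely gain is modest: power at 3 minutes of about 80% to 87% for an additional R² of 2% to 20%, against 79.4% with no covariate credit. Every R², time difference and prevalence used here is an assumption; below an R² of about 5% the precision gain is small.

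The case-mix reason rests on the design, namely runs of ten and a schedule known at the site, and not on chance imbalance. It is a vulnerability, not a demonstrated bias. A reader might conclude that adding the terms would make the comparison safe against selective enrolment. The documents do not support that: adjustment reaches only the case mix that is measured, and leaves predictable allocation and period effects where they are.

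**What to change.** In Section 8, for procedure time:

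1. Pre-specify finding type (calcifications / mass / other) and largest lesion dimension as additional fixed effects.
2. Take both from the existing pre-biopsy imaging or its clinical report, recorded before the biopsy starts. Name who records them. Preferably this is someone who does not know the assigned device, or the values are copied from the existing report, because the site holds the schedule.
3. State which modality takes precedence when several are available, and give a code for findings with no measurable dimension.
4. Keep the model with habitus and location only as a sensitivity analysis.

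**Cost.** Two case report form fields if they are not already there, a short addition to Section 8, and some measurement noise in lesion size. The terms use two degrees of freedom for type and one for size, plus one if the no-dimension code has its own indicator, out of about 400. Fixing the terms in advance also avoids choosing covariates after the data are seen, which matters because Section 5.4.2 foresees use of the results in marketing claims and publications.

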# Figure Legend

- 1. Biopsy device
- Remote control for mode control and arming or firing the biopsy device
- 3. Technologist display
- 4. Imaging display
- 5. Vacuum line assembly and suction canister
- 6. Tissue filter assembly
- 7. Tissue filter drawer
- 8. Footswitch
- 9. Power cord

The user interface for data entry, patient selection, and image acquisition and review is on the Imaging display. The user interface for controlling the modes of the biopsy device are buttons on the Technologist display and on the remote control device. The user interface for arming and firing the biopsy device is on the remote control device. The user rotates the aperture on the biopsy device with the thumbwheel on the disposable biopsy needle. The user adjusts the size of the aperture on the biopsy device by assembling the introducer in one of two preset positions along the needle shaft.

The control devices for this study will be the current devices already used for breast biopsy procedures.

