## 5.2 Primary Endpoint

The primary endpoint of this trial is the measured difference in procedure time between biopsies performed with the Brevera biopsy system with real time imaging and biopsies performed using the standard-of-care biopsy system at each clinical site.

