# 5.3 Secondary Endpoint(s)

Secondary endpoints to be evaluated in this trial include differences in post-biopsy complication rates, total tissue acquisition by number of cores and sample mass, total tissue used by pathology for diagnosis, and the number of discordant biopsies.

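### The ANOVA for number of cores, sample mass and tissue used by pathology names no radiologist term; if device is the only factor, some power is lost on three secondary endpoints

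*Combined protocol and SAP*

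**What the plan says.** Section 8 (Statistical Considerations) handles six endpoints in two ways.

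- Procedure time, post-biopsy complications and discordant biopsies get mixed effects regression. For those analyses "site and radiologist will be considered random effects".
- Number of cores, sample mass and tissue used by pathology "will be compared between the Brevera system and local standard-of-care using Analysis of Variance (ANOVA) testing". Only the device contrast is named. No other section adds a site, radiologist or covariate term for them.

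Section 5.3 lists these tissue measures as secondary endpoints: "total tissue acquisition by number of cores and sample mass, total tissue used by pathology for diagnosis".

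Device is allocated within radiologist. Section 6 (Trial Procedures) says: "Each clinician will complete ten (10) patients in block 1 and ten (10) patients in block 2". Each block is one device, and "A clinician must complete block 1 before moving on to block 2". Section 8 sets the phase 2 size at 7 sites × 3 radiologists × 20 biopsies = 420 subjects, or 210 per device.

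**The concern.** The sponsor expects clustering: the sample size paragraph assumes an intraclass correlation of 0.150 for procedure time. How many cores are taken and how much tissue is removed plausibly depend on the operator as well. Yet the clustering terms are written down for only three of the six endpoints, and no reason is given.

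Each radiologist uses both devices equally, so differences between radiologists cancel out of the device comparison. A device-only ANOVA does not use this. It leaves the between-radiologist variance in the residual and so reports a standard error larger than the true one. The result would be intervals that are too wide and a lower chance of detecting a real difference in tissue yield.

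The open wording also leaves the choice of model until after the data are seen, and the two models give different intervals.

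**Working it through.** **Inputs.** From Section 8: 21 radiologists, 10 cases per device each, 210 per device; for procedure time a 3-minute difference, SD 12, ICC 0.150, alpha 0.05. Two-sided testing is assumed because the plan does not say. The plan gives no ICC, SD or target difference for the tissue endpoints. I therefore borrow the standardised effect for time (3/12 = 0.25 SD) and show an assumed ICC range of 0.05 / 0.15 / 0.30.

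**Step 1: reproduce the plan's power for procedure time.**
- Between-cluster variance removed: SE = 12 × √0.85 × √(2/210) = 1.080; 3/1.080 = 2.779; power = Φ(2.779 − 1.960) = 79% (noncentral t on 398 df: 79.2%). This matches the stated 80% or so.
- ICC ignored and SD 12 used in full: SE = 12 × √(2/210) = 1.171; power = Φ(2.562 − 1.960) = 72.6%. This does not match.

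The plan's own figure thus relies on taking the between-cluster variance out of the error.

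**Step 2: device-only ANOVA, complete 10:10 blocks, constant device effect.** Set the total SD to 1.
- True SE = √((1 − ICC) × 2/210).
- SE used by the device-only ANOVA ≈ √(2/210) = 0.0976.
- Ratio r = 1/√(1 − ICC).
- Type I error = 2 × (1 − Φ(1.96 r)).
- Device-only power = Φ(0.25/true SE − 1.96 r).
- Power with radiologist modelled: noncentral t, 420 − 21 − 1 = 398 df.

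| ICC (assumed) | True SE | r | Type I error, device-only | Power, device-only | Power, radiologist modelled | Loss (points) |
|---|---|---|---|---|---|---|
| 0.05 | 0.0951 | 1.026 | 4.4% | 73.2% | 74.6% | about 1.5 |
| 0.15 | 0.0900 | 1.085 | 3.4% | 74.3% | 79.2% | about 5 |
| 0.30 | 0.0816 | 1.195 | 1.9% | 76.4% | 86.3% | about 10 |

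Both powers rise with the ICC because the total SD is held fixed; the gap between them is what matters. Simulation (40,000 runs) agrees: type I error 4.4% / 3.4% / 2.0%, losses 1.6 / 5.0 / 9.6 points, and intervals about 3% / 8% / 19% too wide. With radiologist modelled, simulated type I error is 5.0% to 5.1%. If an ICC of 0.15 sits at site level instead, simulated power is 74.7% device-only against 79.0% adjusted.

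**Step 3: incomplete blocks (assumed scenario, ICC 0.15).** Suppose k of 21 radiologists stop after block 1, half on each device. Then n per device = 10 × (21 − k) + 5k. The true variance is 2 × 0.85/n + k × (10/n)² × 0.15, and the device-only ANOVA uses about 2/n.
- k = 4: n = 190; true 0.01061, used 0.01053; type I error about 5.1%.
- k = 8: n = 170; true 0.01415, used 0.01176; type I error about 7.4%.

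Simulation with the first device random per radiologist gives about 5% and 7% to 8%. With radiologist as a factor it stays at 4.8% to 5.1%.

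**The case against.** **ANOVA does not mean one-way ANOVA.** With radiologist as a blocking factor, it is an ordinary analysis of this 10:10 design. This stands: the text omits the term but does not exclude it. The defect is an unspecified model, and the losses above apply only under the device-only reading.

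**The effect is small and the inputs are borrowed.** This also stands. Nothing in the plan says that cores or tissue mass cluster as procedure time is assumed to, and no power is claimed for these endpoints.

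**A conservative test makes no false claims.** This is true with complete blocks and a constant effect. Section 6 expects every clinician to finish both blocks, and no drop-out rate is given. Section 13 does allow a site to be closed for low enrolment, so incomplete blocks are possible. With 4 of 21 radiologists affected, though, error is only about nominal.

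**Two stronger readings are tempting.** The first is that ignoring clustering inflates false positives. With device balanced within radiologist and a constant effect, the error runs the other way. The second is that the ANOVA is faulty because the device effect may differ by site. The comparator is indeed local: Section 5.2 refers to "biopsies performed using the standard-of-care biopsy system at each clinical site", and Section 8 plans sub-analyses "if multiple sites utilize the same biopsy system as their standard-of-care device". But the mixed model for the primary endpoint has no such term either, and whether variation counts as error depends on whether inference is to these sites or to a wider population. That is a separate question and no reason to prefer one of the two models compared here.

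**Conclusion.** The point holds as a minor specification gap. Section 8 does not say whether radiologist enters the ANOVA for three secondary endpoints. If it does not, if blocks are complete and if the device effect is constant, the estimate is unbiased. Intervals are then about 3% to 19% too wide, type I error is about 2% to 4.4%, and power falls by about 1.5 to 10 points over an assumed ICC of 0.05 to 0.30 at an assumed effect of 0.25 SD. Under the assumed loss of second blocks, device-only error moves from below 5% to above it, while a model with radiologist holds near 5%.

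A reader might infer that the plan prescribes an invalid test, or that the 80% power for procedure time is in doubt. The documents support neither: the ANOVA sentence leaves room for a radiologist factor, and procedure time has its own mixed model, whose stated power is reproduced.

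**What to change.** Replace the ANOVA sentence in Section 8 with:

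> Number of cores, total sample mass and total tissue used by pathology will be analysed with the mixed effects model specified for procedure time (site and radiologist random).

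If the sponsor prefers to keep ANOVA, state that radiologist within site is a factor. Either wording removes the ambiguity. Adopting the procedure-time model as it stands also brings in its habitus and lesion-location covariates. Nothing here depends on them, so the sponsor should simply say whether they are included.

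The cost is one sentence. The data, enrolment and case report forms are unchanged, and the method is already in the plan. One limit should be known: this model, like the one for procedure time, assumes a common device effect across sites.
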